**Part 3 Hypothesis Testing for Primary Series**

Primary series coprimary endpoint 1: antibody GM value at Day 57

The null hypothesis  $H^1_0$ : immunogenicity response to mRNA-1273, as measured by antibody GM value at Day 57, is inferior in children compared with that in adults ( $\geq 18$  years of age) using mRNA-1273 Study P301 data.

The noninferiority in antibody GM value in children in Part 3 compared with that in adults ( $\geq 18$  years of age) is demonstrated by meeting the following success criterion:

- The lower bound of the (1-alpha) CI of the GMR ruling out 0.67 (lower bound  $\geq 0.67$ ) using a noninferiority margin of 1.5.

The 1-alpha can be 97.5% or 95% depending on the alpha level of 0.025 or 0.05 used for the hypothesis testing. The GMR is the ratio of the GM value of SARS-CoV-2-specific antibody in children receiving mRNA-1273 in this Study P204 compared with the GM value of adults ( $\geq 18$  years of age) receiving mRNA-1273 in Study P301 at Day 57.

Primary series coprimary endpoint 2: antibody seroresponse rate at Day 57

The null hypothesis  $H^2_0$ : immunogenicity response to mRNA-1273 as measured by SRR at Day 57 is inferior in children compared with that in adults ( $\geq 18$  years of age) in Study P301.

The noninferiority in SRR in children receiving mRNA-1273 in Part 3 compared with that in adults ( $\geq 18$  years of age) is demonstrated by meeting the following success criterion:

- The lower bound of the (1-alpha) CI of the SRR difference ruling out -10% (ie, lower bound  $\geq -10\%$ ) using the noninferiority margin of 10%.

The 1-alpha can be 97.5% or 95% depending on the alpha level of 0.025 or 0.05 used for the hypothesis testing. The SRR difference is defined as the SRR in children receiving mRNA-1273 minus the SRR in adults of  $\geq 18$  years of age receiving mRNA-1273 from Study P301.

Part 3 primary series primary immunogenicity objective will be considered to be met if the noninferiority in children compared with the adults ( $\geq 18$  years of age) is demonstrated based on both coprimary endpoints.

### **Part 3 Hypothesis Testing for Third Dose**

#### Third dose coprimary endpoint 1: antibody GM at BD-Day 29

The null hypothesis  $H^1_0$ : immunogenicity response to mRNA-1273 third dose as measured by Ab GM at BD-Day 29 in children in Study P204 is inferior compared with Ab GM that at Day 57 (28 days after Dose 2) in the primary series of mRNA-1273 in adults ( $\geq 18$  years of age) in Study P301.

The noninferiority in Ab GM at BD-Day 29 in children receiving mRNA-1273 as a third dose in Study P204 compared with Ab GM at Day 57 in the primary series in adults ( $\geq 18$  years of age) in Study P301 will be demonstrated by the GMR (1-alpha) CI lower bound  $\geq 0.67$  using a noninferiority margin of 1.5, where the 1-alpha can be 97.5% or 95% depending on the alpha level of 0.025 or 0.05 used for the hypothesis testing. The GMR is defined as the ratio of GM value of Ab at BD-Day 29 in Study P204 compared with Ab GM value at Day 57 (28 days after Dose 2) following the primary series of mRNA-1273 in Study P301.

#### Third dose coprimary endpoint 2: antibody seroresponse rate at BD-Day 29

The null hypothesis  $H^2_0$ : immunogenicity response to mRNA-1273 third dose as measured by SRR at BD-Day 29 in children in Study P204 is inferior compared with SRR at Day 57 (28 days after Dose 2) following the primary series of mRNA-1273 in adults ( $\geq 18$  years of age) in Study P301.

The noninferiority in SRR at BD-D29 in children receiving mRNA-1273 as a third dose in Study P204 compared with SRR at Day 57 (28 days after Dose 2) following the primary series of mRNA-1273 will be demonstrated by the SRR (1-alpha) CI lower bound  $\geq -10\%$  using the noninferiority margin of 10%, where the 1-alpha can be 97.5% or 95% depending on the alpha level of 0.025 or 0.05 used for the hypothesis testing. The SRR difference is defined as the SRR at BD-Day 29 in Study P204 minus the rate at Day 57 (28 days after Dose 2) following the

primary series of mRNA-1273 in adults in Study P301. The SRR is defined as a titer change from baseline (pre-Dose 1) below the LLOQ to  $\geq 4 \times$  LLOQ, or at least a 4-fold rise if baseline is  $\geq$  LLOQ.

Part 3 third dose primary immunogenicity objective will be considered to be met if the noninferiority in the age group compared with the adults ( $\geq 18$  years of age) is demonstrated based on both coprimary endpoints.

Justification of using Immunogenicity Subset of adults ( $\geq 18$  years of age) from Study P301 as a comparator for hypothesis testing

In Phase 3 pivotal Study P301 with more than 30,000 participants enrolled, VE against symptomatic COVID-19 based on adjudication committee assessment starting 14 days after second injection in the PP Set was demonstrated with VE estimate of 93.2% (95% CI: 91.0, 94.8) in adults  $\geq 18$  years in the final efficacy analysis (04 May 2021 database lock) in the blinded phase. In a random sample stratified by baseline SARS-CoV-2 status (negative vs. positive), age group ( $< 65$  vs.  $\geq 65$  years) and race/ethnicity (minority vs. non-minority), there were n=1055 participants  $\geq 18$  years of age in the PP Immunogenicity Subset who received mRNA-1273 100  $\mu$ g with baseline negative SARS-CoV-2 status. The observed pseudovirus neutralizing antibody (PsVNA) ID50 GMT at Day 57 was 1081.1 (95% CI: 1019.8, 1146.1) for adults  $\geq 18$  years in Study P301.

A separate random subset of young adults 18 to 25 years of age from Study P301 (n=305 in the PP Immunogenicity Subset receiving mRNA-1273 100  $\mu$ g, of which n=296 have PsVNA assay results reported at Day 57) was selected for the purpose of immunobridging adolescents in Study P203 and children in Study P204 to young adults in Study P301. This subset of young adults with observed PsVNA ID50 GMT of 1301.3 (95% CI: 1172.3, 1444.5) at Day 57 was planned and used as a comparator in the primary immunogenicity analysis testing the noninferiority of immunogenicity in adolescents in Study P203 and children in Study P204.

The observed Day 57 GMT of 1301.3 in young adults 18 to 25 years is approximately 1.2-fold higher compared with 1081.1 in adults  $\geq 18$  years of age with high VE established (VE estimate of 93.2% [95% CI: 91.0, 94.8]). The data suggest that adults  $\geq 18$  years of age may also be considered as a reference for immunobridging analyses.

If a comparator age group of adults  $\geq 18$  years from Study P301 is used in a primary immunogenicity noninferiority hypothesis testing for children in Study P204, a sensitivity analysis may be performed by using different age group(s) (eg, 18 to 25 years,  $\geq 65$  years) from Study P301 as a comparator.

### 8.3 Power and Sample Size

The initial age groups in Part 1 are for estimation purposes. With approximately 750 participants (approximately 375 participants at each dose level of mRNA-1273) in the initial 6 years to < 12 years age group, there is at least a 90% probability to observe at least 1 participant with an AE at a true AE rate of 1% for a given dose level. In each of the younger age groups (2 years to < 6 years and 6 months to < 2 years), the safety assessment will occur during the conduct of Part 2 after approximately 375 participants have been exposed to mRNA-1273 at the dose level selected for Part 2. For further details, please refer to [Section 7.5.2](#).

The sample size in the expansion (Part 2) is considered to be sufficient to support a safety database in the pediatric participants 6 months to < 12 years of age. With up to 3,000 participants each in the 6 years to < 12 years, 2 years to < 6 years, and 6 months to < 2 years of age groups exposed to mRNA-1273 at a given dose level in Part 2, the study has at least a 95% probability to observe at least 1 participant with an AE at a true 0.1% AE rate for a given dose level.

The sample size in the lower dosing assessment (Part 3) is approximately 300 children 6 years to < 12 years of age receiving mRNA-1273 25 µg. There is at least a 90% probability to observe at least 1 participant with an AE at a true AE rate of 1% in this group.

A subset of Full Analysis Set (FAS) participants (Immunogenicity Subset) in each age group will be selected for measuring immunogenicity data. The immunogenicity samples of the Immunogenicity Subset will be processed, and the analysis of primary immunogenicity endpoint will be based on the PP Immunogenicity Subset.

If a threshold of protection is available, for the primary immunogenicity endpoint, with approximately 289 participants on mRNA-1273 in the PP Immunogenicity Subset of an age group, there will be at least 90% power to rule out 70% with a 2-sided 95% CI (lower bound of the 95% CI > 70%) for the percentage of mRNA-1273 participants exceeding the accepted threshold if the true rate of participants exceeding the threshold is 80%.

If an acceptable antibody threshold of protection against COVID-19 is not available at the time of analysis for the primary immunogenicity endpoint, noninferiority tests of the 2 null hypotheses based on the 2 coprimary endpoints will be performed, respectively. The sample size calculation for each of the 2 noninferiority tests was performed, and the larger sample size was chosen for the study.

- With approximately 289 participants receiving mRNA-1273 in the PP Immunogenicity Subset of each age group in Study P204 and young adults (18 to 25 years of age) in Study P301, there will be 90% power to demonstrate noninferiority of the immune response, as measured by the antibody GM value, in pediatric population at a 2-sided alpha of 0.05, compared with that in young adults (18 to 25 years of age) in Study P301

receiving mRNA-1273, assuming an underlying GMR value of 1, a noninferiority margin of 0.67 (or 1.5), and a point estimate minimum threshold of 0.8. The standard deviation of the natural log-transformed levels is assumed to be 1.5.

- With approximately 289 participants receiving mRNA-1273 in the PP Immunogenicity Subset of each age group in Study P204 and young adults (18 to 25 years of age) in Study P301, there will be at least 90% power to demonstrate noninferiority of the immune response as measured by SRR in children at a 2-sided alpha of 0.05, compared with that in young adults 18 to 25 years of age in Study P301 receiving mRNA-1273, assuming SRR of 85% in young adults of 18 to 25 years of age from Study P301, true SRR of 85% in children (or true rate difference is 0 compared with young adults from Study P301), a noninferiority margin of 10% and a point estimate minimum threshold of -5% in SRR difference.
- In the 1273-P203 interim analysis (data snapshot on 08 May 2021), the observed SRRs at Day 57 were high in both 18 to 25 years of age group from Study P301 (98.6% with 95% CI: 96.6, 99.6) and 12 to 17 years of age group (98.8% with 95% CI: 97.0, 99.7), based on pseudovirus nAb ID50 titers. For this Study P204, if the true SRRs were assumed to be 95% or higher in both 18 to 25 years of age group from Study P301 and an age group in children, with between-group true difference within 4%, there will be a >90% power to demonstrate noninferiority by SRR in children compared with 18 to 25 years of age in Study P301, at a 2-sided alpha of 0.05.
- Assuming approximately 25% of participants in the Immunogenicity Subset in Part 2 will not meet the criteria to be included in the PP Immunogenicity Subset, approximately 528 participants in Part 2 (~396 receiving mRNA-1273 and ~132 receiving placebo) will be selected for the Immunogenicity Subset from which approximately 289 participants on mRNA-1273 will be suitable for the PP Immunogenicity Subset in Part 2.
- In Part 2 for the booster dose primary immunogenicity analysis in an age group, with approximately 289 participants receiving mRNA-1273 booster dose in the PP Immunogenicity Subset with pre-booster negative SARS-CoV-2 in Study P204 and 289 young adults (18 to 25 years of age) receiving mRNA-1273 100 µg primary series in Study P301, there will be a 90% power to demonstrate noninferiority of the immune response, as measured by the antibody GM value, in children receiving a booster dose compared with that in adults (18 to 25 years of age) receiving mRNA-1273 primary series in Study P301, at a 2-sided alpha of 0.05, assuming an underlying true GMR value of 1.0 and a noninferiority margin of 1.5. The standard deviation of the natural log-transformed GMT levels is assumed to be 1.5. Also, if the true SRRs were assumed to be 95% or higher in children receiving mRNA-1273 booster dose in Study P204 and

adults receiving mRNA-1273 primary series in Study P301, with between-group true difference within 4%, there will be a > 90% power to demonstrate noninferiority by SRR in children receiving a booster dose compared with adults receiving primary series in Study P301, at a 2-sided alpha of 0.05.

- In Part 3 for the primary series primary immunogenicity analysis, with approximately 289 participants receiving mRNA-1273 25  $\mu$ g primary series in the PP Immunogenicity Subset in Study P204 and 289 adults ( $\geq$  18 years of age) receiving mRNA-1273 100  $\mu$ g primary series in Study P301, there will be 84% power to demonstrate noninferiority of the immune response, as measured by the antibody GM value, in children compared with that in adults ( $\geq$  18 years of age) receiving mRNA-1273 in Study P301, at a 2-sided alpha of 0.025, assuming a true GMR value of 1.0 and a noninferiority margin of 1.5. The standard deviation of the natural log-transformed GMT levels is assumed to be 1.5. Also, if the true SRRs were assumed to be 95% or higher in children in Study P204 and adults from Study P301, with between-group true difference within 4%, there will be a > 90% power to demonstrate noninferiority by SRR in children compared with adults in Study P301, at a 2-sided alpha of 0.025.
- In Part 3 for the third dose primary immunogenicity analysis, with approximately 289 participants receiving a third dose of mRNA-1273 dose in the PP Immunogenicity Subset with pre-third dose negative SARS-CoV-2 in Study P204 and 289 adults ( $\geq$  18 years of age) receiving mRNA-1273 100  $\mu$ g primary series in Study P301, there will be a 84% power to demonstrate noninferiority of the immune response, as measured by the antibody GM value, in children receiving a third dose compared with that in adults ( $\geq$  18 years of age) receiving mRNA-1273 primary series in Study P301, at a 2-sided alpha of 0.025, assuming an underlying true GMR value of 1.0 and a noninferiority margin of 1.5. The standard deviation of the natural log-transformed GMT levels is assumed to be 1.5. Also, if the true SRRs were assumed to be 95% or higher in children receiving a third dose of mRNA-1273 dose in Study P204 and adults receiving mRNA-1273 primary series in Study P301, with between-group true difference within 4%, there will be a > 90% power to demonstrate noninferiority by SRR in children receiving a third dose compared with adults receiving primary series in Study P301, at a 2-sided alpha of 0.025.

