### Part 1 or 2 Hypothesis Testing for Primary Series in Each Age Group

#### Coprimary endpoint 1: antibody GM value at Day 57

The null hypothesis  $H^1_0$ : immunogenicity response to mRNA-1273, as measured by antibody GM value at Day 57, is inferior in children (in age groups 6 months to < 2 years, 2 years to < 6 years, and 6 years to < 12 years) compared with that in young adults (18 to 25 years of age) using mRNA-1273 Study P301 data.

The noninferiority in antibody GM value in an age group in children compared with that in young adults (18 to 25 years of age) is demonstrated by meeting both success criteria:

- The lower bound of the 95% CI of the geometric mean ratio (GMR) ruling out 0.67 (lower bound  $\geq 0.67$ ) using a noninferiority margin of 1.5, AND
- The GMR point estimate  $\geq 0.8$  (minimum threshold).

The GMR is the ratio of the GM value of SARS-CoV-2-specific antibody in children in an age group receiving mRNA-1273 in this Study P204 compared with the GM value of young adults (18 to 25 years of age) receiving mRNA-1273 in Study P301 at Day 57.

Coprimary endpoint 2: antibody seroresponse rate at Day 57

A definition of seroresponse will be provided in the SAP based on forthcoming information about assay performance.

The null hypothesis  $H^2_0$ : immunogenicity response to mRNA-1273 as measured by SRR at Day 57 is inferior in children compared with that in young adults (18 to 25 years of age) in Study P301.

The noninferiority in SRR in an age group in children compared with that in young adults (18 to 25 years of age) is demonstrated by meeting both success criteria:

- The lower bound of the 95% CI of the SRR difference ruling out -10% (ie, lower bound  $\geq -10\%$ ) using the noninferiority margin of 10%, AND
- The SRR difference point estimate  $\geq -5\%$  (minimum threshold)

The SRR difference is defined as the SRR in children receiving mRNA-1273 minus the SRR in young adults of 18 to 25 years of age receiving mRNA-1273 from Study P301.

The study would be considered to meet the primary immunogenicity endpoint in an age group if the noninferiority in the age group compared with the young adults (18 to 25 years of age) is demonstrated based on both coprimary endpoints.

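### The claim of more than 90% seroresponse power at true differences within 4 points leaves out the required -5% point-estimate criterion; with it, power at a 4-point deficit is about 77% to 81%

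*Protocol*

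**What the plan says.** Section 8.3 (Power and Sample Size) gives two power statements for the primary-series SRR comparison in Parts 1 and 2.

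- The first assumes 85% in both groups. It starts from "With approximately 289 participants receiving mRNA-1273 in the PP Immunogenicity Subset of each age group in Study P204 and young adults", and it names "a noninferiority margin of 10% and a point estimate minimum threshold of -5% in SRR difference".
- The second was added after the adolescent-study interim results (98.6% in young adults, 98.8% in adolescents). It applies "if the true SRRs were assumed to be 95% or higher in both 18 to 25 years of age group from Study P301" and in a pediatric age group, and concludes that "with between-group true difference within 4%, there will be a >90% power to demonstrate noninferiority by SRR in children compared with" young adults, at a two-sided alpha of 0.05. It mentions neither the margin nor the point-estimate threshold. The synopsis repeats it.

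The success rule is in Section 8.2, under the Part 1 or 2 primary series, coprimary endpoint 2. There, "The noninferiority in SRR in an age group in children compared with that in young adults (18 to 25 years of age) is demonstrated" only when two conditions are met together: the 95% CI lower bound for the SRR difference is at least -10%, and the observed difference is at least -5%. Section 8.5.3 repeats both conditions and names the Miettinen-Nurminen score interval.

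**The concern.** The second statement claims power for demonstrating noninferiority, which in this protocol means passing both conditions. A true deficit of 4 points lies only 1 point inside the -5% threshold. With a standard error of about 1.4 points, the observed difference will often fall on the wrong side of that threshold, whatever the confidence interval shows. A figure above 90% is therefore implausible at the far end of the stated range.

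SRR is coprimary. Under the fixed sequence in Section 8.5.3, a failure in the oldest age group stops testing in the younger groups and everything after them. A reader who trusts the sentence would put the risk of failing on SRR at a 4-point deficit below 10%.

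**Working it through.** **Inputs**

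- Group sizes: 289 children and 289 young adults (Section 8.3). The challenged sentence gives no n of its own, so 289 is carried over from the statements before it. As a check, 296 young adults have Day 57 results (Section 8.2, justification of the adult comparator).
- True rates: at least 95% in both groups, differing by at most 4 points (Section 8.3). The least favourable corner is children 95%, adults 99%.
- Success: 95% CI lower bound at least -10% and observed difference at least -5% (Sections 8.2 and 8.5.3).
- Interval: Miettinen-Nurminen score, two-sided 95% (Section 8.5.3).

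**Step 1. Reproduce the 85%/85% statement.** The probabilities of all pairs of responder counts (x children, y adults), each count binomial, are added up over pairs that meet both conditions. The result is 91.6%, in line with the stated figure of at least 90%. So the method matches the protocol's own calculation where the threshold is named.

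**Step 2. Normal approximation at 95% versus 99%.**

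SE = √(0.95×0.05/289 + 0.99×0.01/289) = 0.0141

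- Interval condition alone: Φ((0.10 − 0.04)/0.0141 − 1.96) = Φ(4.26 − 1.96) = 98.9%
- Point-estimate condition: Φ((0.05 − 0.04)/0.0141) = Φ(0.71) = 76.1%

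**Step 3. Exact enumeration, 289 per group.**

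| Children / adults | Deficit (points) | Interval alone | Both conditions |
|---|---|---|---|
| 95% / 97% | 2 | 99.3% | 96.7% |
| 95% / 98% | 3 | 98.0% | 90.6% |
| 96% / 99% | 3 | 99.4% | 93.8% |
| 95% / 98.5% | 3.5 | 96.8% | 85.0% |
| 96% / 99.5% | 3.5 | 98.7% | 89.0% |
| 95% / 98.6% | 3.6 | 96.5% | 83.6% |
| 95% / 99% | 4 | 94.9% | 76.9% |
| 95.5% / 99.5% | 4 | 96.4% | 79.0% |
| 96% / 100% | 4 | 97.5% | 81.4% |

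The 98.6% row uses the young-adult rate quoted in the challenged sentence itself. With 296 adults, 95% versus 99% gives 77.4% for both conditions.

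**Step 4. Compare.** The claim of more than 90% reproduces throughout the 2- to 4-point deficits tabulated on the interval condition alone. At the 4-point corners the joint power equals the probability of meeting the -5% threshold, so that threshold is the binding condition. At 95% versus 99% it is missed in 100% − 76.9% = 23.1% of trials.

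**The case against.** The strongest reply concerns weight rather than arithmetic.

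- *The 77% is the worst corner.* This stands as a point of emphasis. Joint power exceeds 90% up to about 3 points, and the shortfall is confined to roughly the last point of the range. But the protocol itself set the limit at 4 points. All three 4-point corners checked lie below 82%, and reading the limit as strictly less than 4 does not help, since 3.5 points already gives 85% to 89%.
- *The adult comparator has already been observed.* Holding adults fixed at 292 of 296 (an assumed count that matches 98.6%), both conditions are met with probability 86% if the children's true rate is 95%, and 97.5% if it is 96%. This is a useful sensitivity figure, but it is conditional on the adult data and is not the power the sentence describes. At the 95% floor it is still below 90%.
- *Nothing in the design depends on the sentence.* This stands. The figure of 289 rests on the geometric-mean endpoint and the 85%/85% case. The success rule and type I error are untouched. The data that prompted the sentence suggest almost equal rates, where power is high. The fixed-sequence risk applies equally to the geometric-mean endpoint, itself planned at 90%.

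It might also be said that the sentence refers to the interval test only. It does not say so, and the 85%/85% statement just before it counts "a point estimate minimum threshold of -5% in SRR difference" as part of the power.

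**Conclusion.** The stated power is wrong at the limit it sets for itself. Under the protocol's two-part rule, SRR power at a true 4-point deficit is 76.9% at 95% versus 99% and 81.4% at 96% versus 100%, not above 90%. The claim holds only to a deficit of about 3 points with children at 95%, or a little over 3 with children at 96%.

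This assumes 289 per group, independent binomial counts in both groups and the Miettinen-Nurminen interval. The choice of interval hardly matters at 4 points, because the point-estimate condition decides the result. The error is in a power statement for a coprimary endpoint; the sample size and the analysis rule are not in question. The booster and Part 3 criteria in Section 8.2 contain no point-estimate threshold, so this point does not reach their power statements.

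**What to change.** In Section 8.3 and in the matching synopsis text, for the Part 1 and 2 primary series only, do one of the following:

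1. Change the limit on the true difference from 4% to 3%, and say that the power counts both success conditions with about 289 per group (90.6% at 95% versus 98%).
2. Keep the 4% limit, but state that once the -5% point-estimate condition is applied, power at a 4-point deficit is about 77% (95% versus 99%) to 81% (96% versus 100%).

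The cost is one sentence in two places, and a less favourable stated figure. The sample size, success criteria and analysis stay as they are.

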- In Part 3 for the primary series primary immunogenicity analysis, with approximately 289 participants receiving mRNA-1273 25 µg primary series in the PP Immunogenicity Subset in Study P204 and 289 adults ( $\geq 18$  years of age) receiving mRNA-1273 100 µg primary series in Study P301, there will be 84% power to demonstrate noninferiority of the immune response, as measured by the antibody GM value, in children compared with that in adults ( $\geq 18$  years of age) receiving mRNA-1273 in Study P301, at a 2-sided alpha of 0.025, assuming a true GMR value of 1.0 and a noninferiority margin of 1.5. The standard deviation of the natural log-transformed GMT levels is assumed to be 1.5. Also, if the true SRRs were assumed to be 95% or higher in children in Study P204 and adults from Study P301, with between-group true difference within 4%, there will be a > 90% power to demonstrate noninferiority by SRR in children compared with adults in Study P301, at a 2-sided alpha of 0.025.
- In Part 3 for the third dose primary immunogenicity analysis, with approximately 289 participants receiving a third dose of mRNA-1273 dose in the PP Immunogenicity Subset with pre-third dose negative SARS-CoV-2 in Study P204 and 289 adults ( $\geq 18$  years of age) receiving mRNA-1273 100 µg primary series in Study P301, there will be a 84% power to demonstrate noninferiority of the immune response, as measured by the antibody GM value, in children receiving a third dose compared with that in adults ( $\geq 18$  years of age) receiving mRNA-1273 primary series in Study P301, at a 2-sided alpha of 0.025, assuming an underlying true GMR value of 1.0 and a noninferiority

margin of 1.5. The standard deviation of the natural log-transformed GMT levels is assumed to be 1.5. Also, if the true SRRs were assumed to be 95% or higher in children receiving a third dose of mRNA-1273 dose in Study P204 and adults receiving mRNA-1273 primary series in Study P301, with between-group true difference within 4%, there will be a > 90% power to demonstrate noninferiority by SRR in children receiving a third dose compared with adults receiving primary series in Study P301, at a 2-sided alpha of 0.025.

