Modified Intent-to-Treat (mITT) Set	All participants in the FAS who have no serologic or virologic evidence of prior SARS-CoV-2 infection before the first dose of IP (both negative RT-PCR test for SARS-CoV-2 and negative serology test based on bAb specific to SARS-CoV-2 nucleocapsid) at baseline.

Analysis Set	Description
Modified Intent-to-Treat-1 (mITT1) Set	All participants in the mITT Set excluding those who received the wrong treatment (ie, at least 1 dose received that is not as randomized or planned).
Per Protocol Immunogenicity Subset for booster dose or third dose phase	The PP Immunogenicity Subset for booster dose or third dose phase includes participants who received planned booster dose or third dose per schedule, complied with immunogenicity testing schedule, and have no major protocol deviations that impact key or critical data, with pre-booster or pre-third dose negative or positive SARS-CoV-2. The PP Immunogenicity Subset with pre-booster pre-third dose negative SARS-CoV-2 will be used for the primary immunogenicity analysis.

Abbreviations: AR = adverse reaction; bAb = binding antibody; FAS = full analysis set; HAART = highly active anti-retroviral therapy; HIV = human immunodeficiency virus; IP = investigational product; mITT = modified intent-to-treat; mITT1 = modified intent-to-treat-1; PP = per protocol; RT-PCR = reverse transcriptase polymerase chain reaction; SARS-CoV-2 = severe acute respiratory syndrome coronavirus 2.

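### Part 3 power rests on 289 evaluable children out of about 300 enrolled, with no stated loss assumption, although Part 2 plans about 25% loss to reach the same 289

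*Protocol*

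**What the plan says.** Section 8.3 sizes Part 3 first for safety: "The sample size in the lower dosing assessment (Part 3) is approximately 300 children". Figure 1(c) caps the arm at 300, and Table 18 splits it into two sub-cohorts of 150, all bled at Days 1, 57, 149 and 177.

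The Part 3 immunogenicity power is then given for "approximately 289 participants receiving mRNA-1273 25 µg primary series in the PP Immunogenicity Subset in Study P204 and 289 adults" (synopsis wording; Section 8.3 agrees). On that basis "there will be 84% power to demonstrate noninferiority of the immune response, as measured by the antibody GM value, in children compared with" adults, "at a 2-sided alpha of 0.025, assuming a true GMR value of 1.0 and a noninferiority margin of 1.5", with a log-scale SD of 1.5. For SRR the claim is more than 90% if both true rates are at least 95% and differ by no more than 4 points.

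The third-dose statement repeats 84% and more than 90% for "approximately 289 participants receiving a third dose of mRNA-1273 dose in the PP Immunogenicity Subset with pre-third dose negative SARS-CoV-2". Table 10 confirms the restriction: the subset with "pre-third dose negative SARS-CoV-2 will be used for the primary immunogenicity analysis".

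For Part 2, Section 8.3 does allow for loss: "Assuming approximately 25% of participants in the Immunogenicity Subset in Part 2 will not meet the criteria to be included in the PP" Immunogenicity Subset. About 396 vaccine recipients are therefore selected to yield 289. No such allowance is stated for Part 3.

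On the adult side, Section 8.2 and the synopsis justify the comparator aged 18 years or older by a Study P301 sample in which "there were n=1055 participants" in that age range who were per-protocol, received mRNA-1273 and were negative at baseline.

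**The concern.** The same evaluable number, 289, is drawn from about 396 children in Part 2 and from about 300 in Part 3. Table 10 defines the PP Immunogenicity Subset once for all parts. It drops children who are RT-PCR positive or seropositive at baseline, depart from the dosing or sampling schedule, or have major deviations. Exclusion criterion 1 bars only known infection or close contact in the previous two weeks, so children infected earlier can enrol and then leave the set.

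The third-dose set must lose more. A child must also receive Dose 3 three to five months after Dose 2, be SARS-CoV-2 negative before it, and be sampled at BD-Day 29. Using 289 for both analyses assumes no further loss between them.

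At stake is whether a reader can rely on 84% and more than 90% as the power of Part 3. The SRR claim has almost no reserve even at 289, so modest loss matters there.

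**Working it through.** **Inputs from the protocol.** Evaluable children 289; comparator adults 289 (1,055 available); SD 1.5; GM margin 1.5 with true GMR 1.0; SRR margin 10 points with Miettinen-Nurminen limits (Section 8.5.3); two-sided alpha 0.025, so z = 2.2414; Part 3 enrolment about 300; Part 2 loss about 25%.

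**Loss allowed in Part 3.** 1 − 289/300 = 3.7%, or 11 children. In Part 2, 289/396 = 73% are retained. Carrying 25% over gives 300 × 0.75 = 225. To end with 289 at that rate would take 289/0.75, about 386.

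**Formulas.** GM: power = Φ( ln 1.5 / [1.5 × √(1/n₁ + 1/n₂)] − 2.2414 ), with ln 1.5 = 0.4055. SRR: exact sum of binomial probabilities over all outcomes whose Miettinen-Nurminen lower limit is at or above −10 points.

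**Reproducing the plan at 289 against 289.** The GM standard error is 1.5 × √(2/289) = 0.1248, and 0.4055/0.1248 = 3.249. Power = Φ(3.249 − 2.241) = 84.3%, which matches 84%. SRR power is 90.0% at 95% against 99%, the least favourable case inside the stated region, and 99.8% at 95% against 95%.

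**With loss, alpha 0.025, 289 adults:**

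| Loss | Children | GM | SRR 95% v 99% | SRR 95% v 95% |
|---|---|---|---|---|
| 3.7% (as stated) | 289 | 84.3% | 90.0% | 99.8% |
| 10% | 270 | 83.0% | 87.1% | 99.7% |
| 25% (Part 2 rate) | 225 | 78.8% | 79.5% | 99.0% |

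For 225 the GM standard error is 1.5 × √(1/225 + 1/289) = 0.1334, the ratio is 3.040, and Φ(0.799) = 78.8%. Between the extremes, SRR power at 225 is 89.2% for 95% against 98% and 94.0% for 96% against 99%.

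**With all 1,055 adults and 225 children, alpha 0.025.** The GM standard error is 0.1101, the ratio 3.681, and power 92.5%. SRR power at 95% against 99% is 81.4%: more adults barely help, because most of the variance comes from the children.

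**At alpha 0.05.** Under the Part 3 rule in Section 8.5.3, the third dose is tested at 0.05 if the primary series has succeeded at 0.025. With 225 children and 289 adults, GM power is then 86.0% and worst-case SRR power 88.4%. With 1,055 adults they are 95.7% and 89.6%.

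Both coprimary endpoints must succeed, so joint power cannot exceed the lower of the two figures in any row.

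**The case against.** No stated power is miscalculated. The text is conditional on about 289 evaluable children, and both figures reproduce at that number. This stands: what is missing is a loss assumption that makes 289 reachable.

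The 25% is written for Part 2 only. Part 3 is open-label and everyone is bled, so its loss could be smaller; at 10% loss GM power is still 83.0%. This also stands, and is why the 225 figures are conditional. It does not rescue 3.7%, which is stated nowhere and is hard to square with the shared exclusions.

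A reader might infer that both endpoints simply fall to about 79%. The documents do not support that. The SRR figure is one corner of the stated region; elsewhere power is higher, and a Wald calculation would give 94.4% even there, although the protocol names the score method. The SRRs quoted in Section 8.3 from other age groups are 98.6% and 98.8%. On GM, the 1,055 adults give 92.5%. The confidence interval quoted for them (1019.8 to 1146.1) implies an SD of about 0.97, at which GM power with 225 children and 289 adults is about 99%. The 289 adults appear only as a power input; nothing in Section 8.5.3 limits the analysis to them.

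A reader might also infer a much larger third-dose shortfall. The direction is clear, but the protocol gives no figure for the extra loss, and alpha may be 0.05 for that test. Its size cannot be fixed from the document.

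**Conclusion.** The point holds as an unsupported planning input. Both Part 3 power statements need 289 of about 300 children to be evaluable, while the protocol's only loss assumption for this kind of set is about 25%, and the third-dose statement reuses 289 despite added conditions.

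If the Part 2 rate applied, with 289 adults, SD 1.5 and alpha 0.025, GM power would be about 79% rather than 84%. SRR power would range from about 80% at the least favourable rates to about 99% at equal rates of 95%. At 10% loss the worst-case SRR power is 87%, so the claim of more than 90% across the stated region fails even with modest loss. Using all 1,055 adults more than restores GM power but leaves worst-case SRR power at about 81%.

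This does not show that Part 3 is underpowered as it will be run. That depends on the actual loss, the true SRRs, the comparator used and the actual SD.

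**What to change.** In Section 8.3 and the matching synopsis text:

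- State a loss assumption for Part 3 and the evaluable number it gives: about 225 if the Part 2 rate is used, or another rate with its reason.
- Restate power at that number for both coprimary endpoints, giving the SRR rates behind each figure, including 95% against 99%.
- Give the third-dose set a separate, lower number, labelled as an assumption, with power at alpha 0.025 and at 0.05 to match the Part 3 testing rule in Section 8.5.3.
- Base the power and the comparison on all 1,055 evaluable Study P301 adults aged 18 years or older, rather than 289, and say so.

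The cost is wording and a recalculation. The adult data already exist, and no enrolment, margin or success criterion changes. The stated worst-case SRR power will be less favourable than it is now.
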